1 INTRODUCTION

The principal goal of the proposed Phase I/II study is to examine the safety of intracoronary administration of allogeneic cardiosphere-derived cells (CAP-1002) 4 weeks to 12 months following MI.

1.1 Summary of Preclinical Data

1.2 Summary of Clinical Data

1.2.1 Other Cell Therapies

There have been numerous clinical studies to date in which cell therapies have been infused down a coronary artery. The major conclusion of those studies is that the procedure is safe. Efficacy has been a more confounding issue. Bone marrow mononuclear cells (BMMNCs), by far the cell type most extensively studied clinically, have been used repeatedly in acute MI (AMI) patient populations and have shown functional benefits that were marginally positive (Huikuri et al., 2008; Schachinger et al., 2004; Tendera et al., 2009) mixed (Janssens et al., 2006; Roncalli et al., 2011), transient (Meyer et al., 2006; Wollert et al., 2004), or completely negative (Hirsch et al., 2011; Lunde et al., 2006; Wohrle et al., 2010). A meta-analysis of 10 clinical trials involving 698 patients evaluated the overall benefit (Lipinski et al., 2007). Patients receiving cell therapy had an improvement of left ventricular ejection fraction (LVEF) by 3.0% compared to placebo-treated patients. Infarct size and end-systolic volume were significantly reduced in cell-treated patients by 5.6% and 7.4mL, respectively. This analysis and others (Martin-Rendon et al., 2008; Zhang et al., 2009) have also indicated that intracoronary BMMNC therapy has a positive safety profile in AMI patients: no increased incidence of arrhythmias or increased arrhythmia inducibility, no excess proclivity to target- vessel restenosis or repeat revascularization, and no evidence of increased tumorigenesis have been reported. Long-term follow-up data are now emerging from these early studies which also point toward unanticipated benefits on clinical endpoints. In the REPAIR-AMI trial (Schachinger et al., 2006) the incidence of the pre-specified cumulative endpoint of death, MI, or necessity for revascularization was significantly lower at one year. Likewise, the combined endpoint of death, recurrence of MI, and re-hospitalization for heart failure (HF) was reduced. These favorable clinical outcomes were sustained at two years (Assmus et al., 2010). Promising results have also been reported with transplantation of BMMNCs in small trials of patients with chronic cardiomyopathy (Bolli, Jneid, & Dawn, 2005; Dohmann et al., 2005; Perin et al., 2003; Perin et al., 2004; Strauer et al., 2005). However, two rigorous, prospective, randomized, double-blinded studies where autologous BMMNCs were administered either 2- 3 weeks post-MI (LateTIME, (Traverse et al., 2011)) or in a HF population (FOCUS-CCTR, (Perin et al., 2012)), showed no significant benefits on cardiac function or remodeling.

Mesenchymal stem cells (MSCs), or a more selected subset of mesenchymal precursor cells, have been utilized in several clinical studies and can be used from an allogeneic source. Allogeneic MSCs delivered intravenously in AMI patients have shown modest functional improvements (both cardiac and lung as most cells track to the lungs when given intravenously)

in an early phase study (Hare et al., 2009) that has led to a follow-on study. Allogeneic mesenchymal precursor cells have been utilized in patients with HF and shown a significant reduction in MACE (major adverse cardiac events) in treated patients, but inexplicably no dose-effect in the 3 doses tested and no impact on the parameters of cardiac function examined (Perin, 2011). Given the allogeneic nature of the product, PRAs (panel reactive antibodies) and the development of DSAs (donor-specific antibodies) were assessed in this study. Six of 45 patients (13%) developed DSAs against donor HLA class I transiently, with only 2 patients (4%) exhibiting DSAs beyond 1 month, and no patients exhibiting clinical symptoms. Adipose-derived cells (ADCs) can be isolated from autologous sources with some devices under development. ADCs were utilized recently to treat an AMI patient population (APOLLO) and intracoronary infusion led to a respectable reduction in infarct size (Houtgraaf et al., 2012). Intracoronary application of autologous cardiac stem cells (CSCs) in patients after coronary bypass was recently reported as effective in an interim analysis of an early phase study (Bolli et al., 2011).

Collectively, these clinical data 1) show precedence with intracoronary cell infusion and establish a positive safety profile for the delivery method selected for use with CAP-1002; 2) give preliminary evidence that even modest functional benefits can translate into meaningful clinical benefits; 3) point toward a population of post-MI patients who are refractory to therapy with the most commonly used cell type (BMMNCs); 4) create a paradigm for testing an immune response to allogeneic cell products (focused on DSAs 1 month after delivery) and establish expectations as to the immune-related risks involved.

| Term | Percentage |
|------------|------------|
| Organic | 54 |
| Non-GMO | 61 |
| Artificial | 70 |
| Natural | 71 |
| Organic | 72 |
| Non-GMO | 73 |
| Artificial | 74 |
| Natural | 75 |
| Organic | 76 |
| Non-GMO | 77 |
| Artificial | 78 |
| Natural | 79 |
| Organic | 80 |
| Non-GMO | 81 |
| Artificial | 82 |
| Natural | 83 |

1.3.1 Information on CAP -1002

[REDACTED]

[REDACTED]

[REDACTED]

[REDACTED]

1.3.2 Justification for Dose

| Term | Percentage |
|------------|------------|
| GMOs | 85% |
| Organic | 95% |
| Natural | 95% |
| Artificial | 85% |
| Organic | 95% |
| Natural | 95% |
| Artificial | 85% |
| Organic | 95% |
| Natural | 95% |
| Artificial | 85% |

1.3.3 Risks to Human Subjects

[figure not shown]
Risks associated with administration of both the study agent and placebo are similar and related primarily to balloon inflation following catheterization. The risks of balloon inflation are largely related to the balloon inflation pressure. As opposed to the usual clinical setting wherein inflation is performed in the setting of a stenosis and inflation pressures are usually 10-16 atmospheres or higher, inflation in this study is performed within a previously placed stent or area of previous occlusion and solely to prevent reflux of the CAP-1002 or placebo infusion with minimal inflation pressure required to stop blood flow. The risk of coronary dissection is estimated to be less than 1-4% in this setting (Assmus et al., 2006; Janssens, et al., 2006; Schachinger, et al., 2006) and were dissection to occur in a previously unstented segment, a stent would be placed if clinically indicated. In CADUCEUS and ALLSTAR Phase I, no complications that necessitated stent placement were reported during CDC infusion or within 24 hours of infusion among the subjects who were randomized to CDCs.

Other risks of the infusion procedure include those risks that are possible with diagnostic coronary angiography. These include risks related to infection, bleeding, hypotension, pain and hematoma at the arterial puncture site (0.4%), arrhythmia (0.38%), sensitivity or allergy to radiographic contrast (0.37%), exposure to radiation, thromboembolism (0.07%), contrast induced nephropathy, myocardial ischemia or infarction (0.05%). Overall, the risk of any complication is approximately 1.4%, and for death is less than 0.1% (Noto et al., 1991).

| Entity | Percentage |
|----------------|------------|
| Mississippi | 95.0 |
| Alabama | 94.0 |
| Arkansas | 93.0 |
| West Virginia | 92.0 |
| North Carolina | 91.0 |
| South Carolina | 90.0 |
| Virginia | 89.0 |
| Tennessee | 88.0 |
| Missouri | 87.0 |
| Georgia | 86.0 |
| Alabama | 85.0 |
| North Carolina | 84.0 |
| South Carolina | 83.0 |
| Virginia | 82.0 |
| Mississippi | 81.0 |
| Arkansas | 80.0 |
| West Virginia | 79.0 |
| Missouri | 78.0 |
| Georgia | 77.0 |
| Tennessee | 76.0 |
| Alabama | 75.0 |
| Arkansas | 74.0 |
| Mississippi | 73.0 |
| West Virginia | 72.0 |
| Missouri | 71.0 |
| Georgia | 70.0 |
| Tennessee | 69.0 |
| Alabama | 68.0 |
| Arkansas | 67.0 |
| Mississippi | 66.0 |
| West Virginia | 65.0 |
| Missouri | 64.0 |
| Georgia | 63.0 |
| Tennessee | 62.0 |
| Alabama | 61.0 |
| Arkansas | 60.0 |
| Mississippi | 59.0 |
| West Virginia | 58.0 |
| Missouri | 57.0 |
| Georgia | 56.0 |
| Tennessee | 55.0 |
| Alabama | 54.0 |
| Arkansas | 53.0 |
| Mississippi | 52.0 |
| West Virginia | 51.0 |
| Missouri | 50.0 |
| Georgia | 49.0 |
| Tennessee | 48.0 |
| Alabama | 47.0 |
| Arkansas | 46.0 |
| Mississippi | 45.0 |
| West Virginia | 44.0 |
| Missouri | 43.0 |
| Georgia | 42.0 |
| Tennessee | 41.0 |
| Alabama | 40.0 |
| Arkansas | 39.0 |
| Mississippi | 38.0 |
| West Virginia | 37.0 |
| Missouri | 36.0 |
| Georgia | 35.0 |
| Tennessee | 34.0 |
| Alabama | 33.0 |
| Arkansas | 32.0 |
| Mississippi | 31.0 |
| West Virginia | 30.0 |
| Missouri | 29.0 |
| Georgia | 28.0 |
| Tennessee | 27.0 |
| Alabama | 26.0 |
| Arkansas | 25.0 |
| Mississippi | 24.0 |
| West Virginia | 23.0 |
| Missouri | 22.0 |
| Georgia | 21.0 |
| Tennessee | 20.0 |
| Alabama | 19.0 |
| Arkansas | 18.0 |
| Mississippi | 17.0 |
| West Virginia | 16.0 |
| Missouri | 15.0 |
| Georgia | 14.0 |
| Tennessee | 13.0 |
| Alabama | 12.0 |
| Arkansas | 11.0 |
| Mississippi | 10.0 |
| West Virginia | 9.0 |
| Missouri | 8.0 |
| Georgia | 7.0 |
| Tennessee | 6.0 |
| Alabama | 5.0 |
| Arkansas | 4.0 |
| Mississippi | 3.0 |
| West Virginia | 2.0 |
| Missouri | 1.0 |
| Georgia | 0.0 |

| Entity | Percentage |
|------------------|------------|
| Mississippi | 92.0 |
| Alabama | 89.5 |
| North Dakota | 89.0 |
| South Dakota | 88.5 |
| Arkansas | 88.0 |
| Montana | 87.5 |
| Wyoming | 87.0 |
| Illinois | 86.5 |
| West Virginia | 86.0 |
| Michigan | 85.5 |
| Missouri | 85.0 |
| Virginia | 84.5 |
| Washington | 84.0 |
| Utah | 83.5 |
| Arizona | 83.0 |
| Colorado | 82.5 |
| Connecticut | 82.0 |
| Massachusetts | 81.5 |
| Washington, D.C. | 81.0 |
| Delaware | 80.5 |
| New Jersey | 80.0 |
| Washington | 79.5 |
| Florida | 79.0 |
| Georgia | 78.5 |
| Tennessee | 78.0 |
| North Carolina | 77.5 |
| South Carolina | 77.0 |
| Ohio | 76.5 |
| Indiana | 76.0 |
| Pennsylvania | 75.5 |
| Michigan | 75.0 |
| Wisconsin | 74.5 |
| Minnesota | 74.0 |
| Missouri | 73.5 |
| Mississippi | 73.0 |
| Alabama | 72.5 |
| North Dakota | 72.0 |
| South Dakota | 71.5 |
| Arkansas | 71.0 |
| Montana | 70.5 |
| Wyoming | 70.0 |
| Illinois | 69.5 |
| West Virginia | 69.0 |
| Michigan | 68.5 |
| Missouri | 68.0 |
| Virginia | 67.5 |
| Washington | 67.0 |
| Utah | 66.5 |
| Arizona | 66.0 |
| Colorado | 65.5 |
| Connecticut | 65.0 |
| Massachusetts | 64.5 |
| Washington, D.C. | 64.0 |
| Delaware | 63.5 |
| New Jersey | 63.0 |
| Washington | 62.5 |
| Florida | 62.0 |
| Georgia | 61.5 |
| Tennessee | 61.0 |
| North Carolina | 60.5 |
| South Carolina | 60.0 |
| Ohio | 59.5 |
| Indiana | 59.0 |
| Pennsylvania | 58.5 |
| Michigan | 58.0 |
| Wisconsin | 57.5 |
| Minnesota | 57.0 |
| Mississippi | 56.5 |
| Alabama | 56.0 |
| North Dakota | 55.5 |
| South Dakota | 55.0 |
| Arkansas | 54.5 |
| Montana | 54.0 |
| Wyoming | 53.5 |
| Illinois | 53.0 |
| West Virginia | 52.5 |
| Michigan | 52.0 |
| Missouri | 51.5 |
| Virginia | 51.0 |
| Utah | 50.5 |
| Arizona | 50.0 |
| Colorado | 49.5 |
| Connecticut | 49.0 |
| Massachusetts | 48.5 |
| Washington, D.C. | 48.0 |
| Delaware | 47.5 |
| New Jersey | 47.0 |
| Washington | 46.5 |
| Florida | 46.0 |
| Georgia | 45.5 |
| Tennessee | 45.0 |
| North Carolina | 44.5 |
| South Carolina | 44.0 |
| Ohio | 43.5 |
| Indiana | 43.0 |
| Pennsylvania | 42.5 |
| Michigan | 42.0 |
| Wisconsin | 41.5 |
| Minnesota | 41.0 |
| Mississippi | 40.5 |
| Alabama | 40.0 |
| North Dakota | 39.5 |
| South Dakota | 39.0 |
| Arkansas | 38.5 |
| Montana | 38.0 |
| Wyoming | 37.5 |
| Illinois | 37.0 |
| West Virginia | 36.5 |
| Michigan | 36.0 |
| Missouri | 35.5 |
| Virginia | 35.0 |
| Utah | 34.5 |
| Arizona | 34.0 |
| Colorado | 33.5 |
| Connecticut | 33.0 |
| Massachusetts | 32.5 |
| Washington, D.C. | 32.0 |
| Delaware | 31.5 |
| New Jersey | 31.0 |
| Washington | 30.5 |
| Florida | 30.0 |
| Georgia | 29.5 |
| Tennessee | 29.0 |
| North Carolina | 28.5 |
| South Carolina | 28.0 |
| Ohio | 27.5 |
| Indiana | 27.0 |
| Pennsylvania | 26.5 |
| Michigan | 26.0 |
| Wisconsin | 25.5 |
| Minnesota | 25.0 |
| Mississippi | 24.5 |
| Alabama | 24.0 |
| North Dakota | 23.5 |
| South Dakota | 23.0 |
| Arkansas | 22.5 |
| Montana | 22.0 |
| Wyoming | 21.5 |
| Illinois | 21.0 |
| West Virginia | 20.5 |
| Michigan | 20.0 |
| Missouri | 19.5 |
| Virginia | 19.0 |
| Utah | 18.5 |
| Arizona | 18.0 |
| Colorado | 17.5 |
| Connecticut | 17.0 |
| Massachusetts | 16.5 |
| Washington, D.C. | 16.0 |
| Delaware | 15.5 |
| New Jersey | 15.0 |
| Washington | 14.5 |
| Florida | 14.0 |
| Georgia | 13.5 |
| Tennessee | 13.0 |
| North Carolina | 12.5 |
| South Carolina | 12.0 |
| Ohio | 11.5 |
| Indiana | 11.0 |
| Pennsylvania | 10.5 |
| Michigan | 10.0 |
| Wisconsin | 9.5 |
| Minnesota | 9.0 |
| Mississippi | 8.5 |
| Alabama | 8.0 |
| North Dakota | 7.5 |
| South Dakota | 7.0 |
| Arkansas | 6.5 |
| Montana | 6.0 |
| Wyoming | 5.5 |
| Illinois | 5.0 |
| West Virginia | 4.5 |
| Michigan | 4.0 |
| Missouri | 3.5 |
| Virginia | 3.0 |
| Utah | 2.5 |
| Arizona | 2.0 |
| Colorado | 1.5 |
| Connecticut | 1.0 |
| Massachusetts | 0.5 |
| Washington, D.C. | 0.0 |

1.4

2 STUDY OBJECTIVES

2.1 Primary Safety Objective

The primary safety objective is to determine the safety profile of CAP-1002 administered by intracoronary infusion in subjects with ischemic left ventricular dysfunction and a previous myocardial infarction (MI); specifically, to test the null hypothesis that the incidence rate of the primary safety endpoint (a composite of peri-procedural clinical events) differs by no more than 0.20 between treatment groups.

2.2 Primary Efficacy Objective

The primary efficacy objective is to evaluate whether administration of CAP-1002 by intracoronary infusion may result in structural cardiac benefits for subjects with ischemic left ventricular dysfunction and a previous MI as measured by infarct size expressed as a percent of left ventricular mass 12 months after infusion; specifically, to test the hypothesis that CAP-1002 is superior to placebo in reducing infarct size, expressed as a percent of left ventricular mass, 12 months after infusion, either in all subjects combined or in subjects with recent MI (≤ 90 days before infusion).

2.3 Secondary Objectives

The secondary safety objective is to compare the safety profiles of CAP-1002 and placebo over 12 months based on pre-specified clinical events and development of increased HLA antibody levels.

The secondary efficacy objective is to evaluate whether administration of CAP-1002 by intracoronary infusion may result in other left ventricular structural or functional cardiac benefits for subjects with ischemic left ventricular dysfunction and a previous MI. Also evaluations will investigate whether administration of CAP-1002 may result in clinical or biomarker benefits for subjects with ischemic left ventricular dysfunction and a previous MI.

2.4 Safety Assessments

The primary safety endpoint is the one-month post intracoronary infusion proportion of subjects

experiencing any of the following adjudicated events:

1. Acute myocarditis possibly attributable to CAP-1002 or placebo, diagnosed with consideration of clinical context, with or without a clinically indicated endomyocardial biopsy. In order to be considered related to CAP-1002 or placebo, humoral or cellular immune reaction specific to CAP-1002 must also be documented for subjects treated with CAP-1002, or a temporal relationship with IP administration must exist for subjects administered placebo.
2. Death due to ventricular tachycardia or ventricular fibrillation defined as occurring with ECG documentation of these arrhythmias during ambulatory ECG monitoring in an outpatient setting, or during routine ECG monitoring while hospitalized.
3. Sudden unexpected death defined as occurring within one hour of symptom onset, or un-witnessed death in a person previously observed to be well within the preceding 24 hours without an identified cause.
4. Major adverse cardiac event (MACE), defined as the composite incidence of death, non- fatal recurrent MI, hospitalization for heart failure, emergency room treatment for heart failure (NT-proBNP >450 pg/mL or BNP>100 pg/ml, with treatment including intravenous diuretic administration), left ventricular assist device (LVAD) placement or heart transplant. Peri-infusion MI will be defined as presence of troponin or CK-MB levels > 5 times the upper reference limit during the 24 hours following infusion. These elevations must be accompanied by symptoms of ischemia > 20 minutes in duration and ECG changes indicative of new ischemia (new ST-T changes or new left bundle branch block), development of pathological Q waves on the ECG, imaging evidence of new loss of viable myocardium, or new regional wall motion abnormality.

Separate strata will be evaluated for subjects with a Recent MI and with a Chronic MI. The following adjudicated events will be evaluated as secondary safety endpoints during the twelve-month follow-up period:

1. Acute myocarditis possibly attributable to CAP-1002 or placebo, diagnosed with consideration of clinical context, with or without a clinically indicated endomyocardial biopsy. In order to be considered related to CAP-1002 or placebo, humoral or cellular immune reaction specific to CAP-1002 must also be documented for subjects treated with CAP-1002, or a temporal relationship with IP administration must exist for subjects administered placebo.
2. Death due to ventricular tachycardia or ventricular fibrillation defined as occurring with prior ECG documentation of these arrhythmias during ambulatory ECG monitoring in an outpatient setting or during routine ECG monitoring while hospitalized.
3. Sudden unexpected death defined as occurring within one hour of symptom onset, or un-witnessed death in a person previously observed to be well within the preceding 24 hours without an identified cause.
4. Major adverse cardiac event (MACE), defined as the composite incidence of death, non- fatal recurrent MI, hospitalization for heart failure, emergency room treatment for heart failure (NT-proBNP >450 pg/mL or BNP>100 pg/ml, with treatment including intravenous diuretic administration), left ventricular assist device (LVAD) placement or heart transplant. Peri-infusion MI will be defined as presence of troponin or CK-MB levels > 5 times the upper reference limit during the 24 hours following infusion. These elevations must be accompanied by symptoms of ischemia > 20 minutes in duration and ECG changes indicative of new ischemia (new ST-T changes or new left bundle branch block), development of

pathological Q waves on the ECG, imaging evidence of new loss of viable myocardium, or new regional wall motion abnormality.

5. New cardiac tumor formation on MRI imaging.
6. Any hospitalization due to a cardiovascular cause or related to CAP-1002 or placebo infusion.
7. Any inter-current cardiovascular illness or one related to CAP-1002 infusion or placebo, which prolongs hospitalization. Evidence of myocardial injury will be assessed by a rule out MI cardiac enzyme protocol performed following administration of CAP-1002 or placebo. Troponin and CK-MB will be obtained approximately every 8 hours for the first 24 hours after infusion.
8. New TIMI flow ≤ 1 , following intracoronary infusion of CAP-1002 or placebo.
9. Development of, or an increase in the frequency of, ventricular tachycardia with a duration of 30 beats or longer ascertained by periodic, protocol-mandated 24 hour ambulatory ECG monitoring.
10. Development of increased anti-HLA antibody levels with development of sensitization to HLA antigens specific to the CAP-1002 CDC donor.

2.4.1 Efficacy Assessments

The primary efficacy endpoint is the percent change from baseline in MRI assessment of infarct size as a percent of left ventricular mass 12 months after administration of treatment (either CAP-1002 or placebo). The following will be evaluated as secondary efficacy endpoints during the six-month and twelve-month follow-up periods:

Global LV Function Measures

1. Percent change and change from baseline in MRI assessment of LVEF
2. Percent change and change from baseline in MRI assessment of left ventricular end-diastolic and end-systolic volumes indexed to BSA

Structural measures

3. Change from baseline in MRI assessment of infarct size as a percent of left ventricular mass
4. Percent change and change from baseline in MRI assessment of infarct size expressed in grams
5. Percent change and change from baseline in MRI assessment of viable mass expressed in grams

Regional measure

6. Percent change and change from baseline in MRI assessment of function in the region which received CAP-1002 therapy

Clinical function/status measures

7. Percent change and change from baseline in distance covered in six minute walk test
8. Change from baseline in Minnesota Living with Heart Failure Questionnaire (MLHFQ) scores (Total score, Physical Dimension score, and Emotional Dimension score)
9. Change from baseline in Patient Global Assessment (PGA) score

Biomarker

10. Percent change and change from baseline in NT-proBNP
11. Change from baseline in log transformed NT-proBNP

Additional detail regarding secondary endpoint analyses can be found in the SAP.

[figure not shown]
2.5 Exploratory Assessments

2.5.1 Presence of DSAs (mismatched) against all donors

The exploratory analysis is designed to evaluate the prevalence of mismatched subjects within the Randomized Cohort, as well as, the safety and efficacy profiles within the enrolled population. This group of subjects will be called the Exploratory Randomized Cohort. A review and descriptive comparison of safety and efficacy between the Randomized Cohort and the Exploratory Randomized Cohort group will be performed, which preserves the design integrity and statistical power of the Randomized Cohort.

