
Up to approximately 103 subjects will be enrolled in the Primary Randomized Cohort. This maximum sample size is based on the Recent and Chronic MI strata being analyzed independently with a treatment effect of 15% at Month 12 for each strata, a pooled standard deviation of 10%, a minimum power of 80%, and a significance level (alpha) of 0.05. The double-blind, placebo-controlled design of the Primary Randomized Cohort will maximize the study's ability to assess both safety and efficacy, as both may be subject to bias from the perspective of Investigators and subjects.

The Exploratory Randomized Cohort will enroll up to 17 subjects in addition to the Primary Randomization Cohort. Exploratory Randomized Cohort subjects are those subjects who are mismatched against all available donors. The Exploratory Randomized Cohort will also include Recent and Chronic subjects (up to n=8-9 per stratum). The Exploratory Randomized Cohort will be randomized in a double-blind fashion as described in the Primary Randomized Cohort. The Exploratory Randomized Cohort will undergo the same tests as all other subjects based on the schedule of events (see [Appendix 1](#) Schedule of Events Table). This group will be analyzed

separately from the Primary Randomized Cohort (n=103) using descriptive analyses to assess the prevalence and impact on safety and efficacy, if any. The Exploratory Randomized Cohort sample size was estimated based on DSA results observed in the Safety Cohort, where approximately 14% of the screened subjects would have been mismatched to all available donors, i.e., assuming at 14% rate of mismatch, approximately 120 subjects would be screened to achieve enrollment of 103 in the matched Primary Randomized Cohort, thus yielding up to 17 subjects enrolled in the mismatched Exploratory Randomized Cohort.

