4 STUDY POPULATION SELECTION

4.1 Study Population

Approximately 134 subjects with a history of MI and angioplasty that resulted in a patent infarct-related artery, with stent placement, will be enrolled in this study. These subjects will be primarily recruited from subjects referred to the Principal Investigator at each study site. Of the 134 subjects enrolled, 14 will be part of a Safety Cohort to examine safety of administration of CAP-1002 one month following infusion (followed for 12 months) and up to approximately 103 will be included in the Primary Randomized Cohort. It is anticipated that up to 93 randomized subjects within the Primary Randomized Cohort will complete the study through the 12 month follow up period. The study will enlist approximately 45 sites for participation. Up to 17 additional subjects may be treated as part of the Exploratory Randomized Cohort. However, since this group is exploratory in nature, enrollment of the Primary Randomized Cohort will define the end of the study; that is, once the Primary Randomized Cohort is fully enrolled, the study will be considered closed for further subject enrollment.

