5 STUDY TREATMENT(S)

5.1 Description of Treatment(s)

5.1.1 Study Drug

CAP-1002 CDCs will be grown from donors unrelated to the recipients. While the HLA type of the recipient subject and the CAP-1002 donor CDCs will be tested and known, primarily for product identification purposes, matching of the donors and subjects will not be performed. Subjects will be assessed for anti-HLA antibodies at screening, but will not be excluded from the study based on the presence of DSAs. Subjects, who can be matched, in the sense that no DSAs are present to one or more donors, will be enrolled in the Primary Randomized Cohort. Subjects, who are mismatched against all available donors, because they harbor one or more anti-HLA antibody against each donor, will be enrolled in the Exploratory Randomized Cohort. Subjects who receive the Investigational Product (IP) (CAP-1002 or placebo) will be monitored during the course of the study for development of increased anti-HLA antibody levels with development of sensitization to HLA antigens specific to the CAP-1002 CDC donor (i.e. DSAs). The IP is delivered to the clinical sites on an as-needed, per subject basis.

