| | Mean | SD | Mean | SD |
| CAP-1002 Recent | 6.20 | 10.00 | 14.70 | 10.00 |
| CAP-1002 Chronic | 3.10 | 10.00 | 7.35 | 10.00 |
| Placebo | 0.00 | 10.00 | 0.00 | 10.00 |

Power calculations using Monte Carlo simulation indicated that, under these assumptions, the trial will have more than 90% power to be declared successful with a total sample size of 100.

Primary Randomized Cohort

The Primary Randomized Cohort is designed to assess the efficacy of the study agent as well as further evaluate the safety profile of CAP-1002. Up to 103 subjects will be enrolled in the Primary Randomized Cohort. This maximum sample size is based on the Recent and Chronic MI strata being analyzed independently with a treatment effect of 15% at Month 12 for each strata, a pooled standard deviation of 10%, a minimum power of 80%, and a significance level (alpha) of 0.05.

Exploratory Randomized Cohort

The Exploratory Randomized Cohort sample size of up to 17 subjects was estimated based on DSA results observed in the Safety Cohort, where approximately 14% of the screened subjects had pre-formed antibodies to all available donors. That is, assuming a 14% rate of pre-formed DSAs, approximately 120 subjects would be screened to achieve enrollment of 103 in the matched Primary Randomized Cohort, thus yielding up to 17 subjects enrolled in the Exploratory Randomized Cohort. Enrollment into the Exploratory Randomized Cohort is capped at n=17, with no pre-specified limit for subject counts in the Recent and Chronic stratum. Enrollment in the study will be complete when the Primary Randomized Cohort is fully enrolled, regardless of whether the Exploratory Randomized Cohort has enrolled.

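### Prevalence of donor mismatch is to be evaluated within the randomised subjects, but the cap of 17 limits that fraction to about 14.2% once the Primary Randomized Cohort fills, so a higher rate could not show

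*Protocol*

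**What the plan says.** Protocol Section 2.5.1 gives the aim and its denominator: "The exploratory analysis is designed to evaluate the prevalence of mismatched subjects within the Randomized Cohort". Section 3.1 repeats the aim for the Exploratory Randomized Cohort, which is to be analysed "using descriptive analyses to assess the prevalence and impact on safety and efficacy, if any". The synopsis also names prevalence, but does not attach the words about the Randomized Cohort to it.

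Three design features then bear on that fraction:

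- **Cap on mismatched subjects** (Section 9.2): "Enrollment into the Exploratory Randomized Cohort is capped at n=17".
- **Matched target** (Section 9.2): "Up to 103 subjects will be enrolled in the Primary Randomized Cohort". Elsewhere the number is given as approximate.
- **End of enrolment** (Section 4.1): "once the Primary Randomized Cohort is fully enrolled, the study will be considered closed for further subject enrollment".

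Section 9.2 derives the cap from a planning rate: "assuming a 14% rate of pre-formed DSAs, approximately 120 subjects would be screened to achieve enrollment of 103 in the matched Primary Randomized Cohort". Section 3.1 attributes that rate to screened subjects in the Safety Cohort. On DSA testing, Section 5.1.1 says: "Subjects will be assessed for anti-HLA antibodies at screening, but will not be excluded from the study based on the presence of DSAs".

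The SAP adds no prevalence analysis. Section 8 limits study-population listings to the ITT populations, which contain randomised subjects only, and plans the summaries for the primary mITT population, which contains no Exploratory cohort subjects; summaries in other populations are optional. Section 8.6 covers screening laboratory and HLA results within those limits. Appendix C has listings for HLA profile and DSA monitoring but no prevalence table.

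**The concern.** With the denominator that Section 2.5.1 names, the numerator is limited by the cap and the rest of the denominator by the matched target. The design therefore sets an upper limit on the quantity to be described, and that limit is almost exactly the rate assumed in planning. A mismatch rate well above 14% would come out close to 14% and could be taken as agreement with the Safety Cohort figure. The error runs in one direction only: too low.

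The change of denominator also makes the comparison awkward. The 14% is a fraction of screened subjects; Section 2.5.1 asks for a fraction of randomised subjects. Neither document says how a mismatched subject found after the 17th is recorded. If those DSA results are not kept, a higher rate could not be recovered from the full screening experience afterwards.

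**Working it through.** **Inputs.** From Protocol Section 9.2: matched target 103, cap 17, planning rate 14%, about 120 screened. From Section 4.1: enrolment closes when the Primary Randomized Cohort is full.

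**Step 1. Reproduce the plan's own figures.** Screened = 103/(1 − 0.14) = 119.8, which rounds to the stated 120. Mismatched = 119.8 − 103 = 16.8, which rounds to the stated 17. Both agree.

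**Step 2. Ceiling on the randomised fraction.** Ceiling = cap/(cap + matched) = 17/(17 + 103) = 17/120 = 14.2%. Because 103 is approximate, other matched totals were tried (assumed values):

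| Matched enrolled | Ceiling |
|---|---|
| 90 | 17/107 = 15.9% |
| 100 | 17/117 = 14.5% |
| 103 | 17/120 = 14.2% |
| 110 | 17/127 = 13.4% |

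**Step 3. Effect of the cap at different true rates.** Let X be the number of mismatched subjects who present before the 103rd matched one. If consecutive eligible subjects are mismatched with constant probability p, X is negative binomial with mean 103p/(1 − p). The fraction reported is min(X, 17)/(103 + min(X, 17)); without the cap it would be X/(103 + X).

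| True rate p | Mean X | P(X > 17) | Mean reported, with cap | Mean without cap |
|---|---|---|---|---|
| 10% | 11.4 | 0.05 | 9.8% | 9.9% |
| 14% | 16.8 | 0.42 | 12.8% | 13.9% |
| 20% | 25.8 | 0.94 | 14.1% | 19.8% |
| 25% | 34.3 | 0.997 | 14.2% | 24.8% |
| 30% | 44.1 | >0.999 | 14.2% | 29.8% |

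At 10% the cap makes almost no difference. At the planning rate it turns subjects away in about 4 trials in 10, and the mean falls about 1 point. From 20% upward the result is nearly constant, so 20% and 30% could not be told apart.

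**Step 4. Does the SAP change the ceiling?** SAP Section 3 gives approximately 17 mismatched subjects with no stated cap, about 120 enrolled, and an end of enrolment at about 130 randomised. With 130 randomised and 17 mismatched, the fraction is 17/130 = 13.1%. With 103 matched, 130 leaves 27 mismatched and 27/130 = 20.8%, but 27 would breach the protocol cap. The two documents need reconciling; the SAP does not remove the limit that the protocol sets.

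**The case against.** The strongest reply is that neither document defines an estimator. Where the protocol does quote a mismatch rate, it uses screened subjects; the synopsis does not tie prevalence to the randomised subjects; and DSA status is known before cohort assignment (SAP Section 5). On that reading the only fault is an unspecified denominator. This stands in part: a screened denominator is feasible and closer to the protocol's own usage. But Section 2.5.1 does name a denominator, and following it truncates the result, while neither document plans the screened version.

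A second reply is that the cap censors only after the 17th mismatched subject. Randomisation dates are listed (SAP Sections 8.8 and 8.9), so a cohort that filled early would be visible. At a true 30% the 17th would be expected near subject 17/0.30 = 57, and the share up to that point would be near 30%. This is right, but no such calculation is planned.

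A third reply concerns size. At 14% the shortfall of about 1 point is small beside a binomial standard error of √(0.14 × 0.86/120) = 3.2 points. Serious distortion needs a true rate well above the only figure the documents give. That also stands.

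Three stronger readings are tempting, and the documents do not support them:

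- **That the study cannot report more than 14.2% whatever happens.** The ceiling holds for the randomised fraction, with the Primary cohort at 103 and the cap observed.
- **That the cap contradicts Section 5.1.1 by excluding subjects because of DSAs.** The protocol does not say what happens to a mismatched subject after the 17th, so the conflict is an inference.
- **That the rate decides how many patients a donor bank could serve.** Nothing in the documents says so.

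**Conclusion.** The concern holds in a limited form. If the Primary Randomized Cohort fills at about 103 and the protocol cap is kept, the fraction named in Section 2.5.1 cannot exceed about 14.2%. The bias is negligible at a true 10%, about 1 point at 14%, and large from 20% upward (20% appears as 14.1%, 30% as 14.2%).

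These means rest on a constant mismatch rate among consecutive eligible subjects. Mismatch is defined against all available donors, so the rate could shift if the donor set changes. The ceiling itself does not depend on that assumption.

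The aim is exploratory and descriptive. No hypothesis, stopping guideline, or primary or secondary analysis uses the prevalence figure, and a reader should not infer that the main results are at risk. It is still worth correcting, because the remedy is cheap and has to be set up before screening results are lost.

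**What to change.** - **Protocol Section 2.5.1 and synopsis.** Define prevalence as subjects mismatched to all available donors, divided by all screened subjects with a screening DSA result, whether or not enrolled and including any found after the cap is reached.
- **SAP.** Add one table with that proportion and an exact 95% confidence interval. Report the randomised fraction (at most 17 of about 120) only as an enrolment count.
- **Reconcile the numbers.** Bring the protocol cap of 17 and total of about 120 into line with SAP Section 3, which gives approximately 17 mismatched and both about 120 and about 130 subjects.

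The cost is wording and one table. DSA is already tested at screening and already determines the cohort, so no extra subjects, samples or assays are needed. The small downside is that DSA results of screen failures must be kept in the database.
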